5 PRIMARY, SECONDARY AND EXPLORATORY ENDPOINTS

5.1 Primary Endpoint

The **primary endpoint** of study is:

Duration of episode (DOE) will be measured in hours (using the Science 37 Platform), of a single treated HL lesion. Observation period to determine healing will last up to 14 days. DOE is defined in detail in section 4.

5.2 Secondary Endpoints

Following are the **secondary endpoints** of the study:

- Incidence of aborted lesions, defined as treated HL lesions that do not progress to the vesicular or crust stage. Observation period to determine healing will last up to 14 days.
- > Incidence of recurrence of HL lesions during the 12-month follow-up period.
- > Time to recurrence of HL lesions, measured in days from resolution of the cold sore treated in the Treatment phase until appearance of a cold sore during the follow-up period.
- ➤ The percentage of subjects who have at least one recurrence during the 12-month follow up period.
- > Safety and tolerability measured by the incidence of Treatment-Emergent Adverse Events (TEAEs).

CONFIDENTIAL Page 19 of 31

Private and Confidential Study No 21755 Date: DEC 18, 2023

5.3 Other Endpoints

Following are the **other endpoints** of the study:

- ➤ Duration of episode (DOE) will be measured in hours (using the Science 37 Platform), of a single treated HL lesion in subjects who initiation study intervention within 1 hour of onset of prodromal symptoms and subjects who initiated study intervention more than 1 hour after onset of prodromal symptoms.
- Time to cessation of symptoms, measured in hours from initial application of assigned study intervention. Cessation of symptoms is defined as the absence of sensations of pain, tenderness tingling, itching or discomfort at the site of the cold sore as measured by NRS.
- ➤ Quality of life score, as measured by the OHIP-14 questionnaire at 3-, 7- and 14-days post-dose.
- ➤ Global assessment of study intervention at Day 14.
- > The change from baseline to post-dose in NRS.
- The incidence of detachment or swallowing within 6 hours of dosing and the number (percentage) of subjects with the incidence.
- ➤ The percentage of subjects who replace the tablet among those with detachment or swallowing within 6 hours of dosing.

6 ANALYSIS POPULATION AND TREATMENT GROUPS

6.1 Analysis Population

Screened Population: All subjects who signed the Informed Consent Form.

Safety Population: All randomized subjects who take at least one dose of IMP.

Intent-to-treat (ITT) Population: All subjects who are randomized and provide at least one measure of primary efficacy parameters after the first dose of IMP i.e., if there is at least one non-missing assessment of subject's face image using a 6-point Likert scale after study drug initiation.

PP Population: The Per Protocol population will include all subjects in ITT who complete 14-days of evaluations and do not have any major protocol violations. Any exclusion from PP Population will be determined and documented prior to the database lock.

Follow-Up Population: The Follow Up population will be a subgroup of the ITT population who will continue into the 12 month follow up period and will be defined as patients whose lesions were all treated at the end of the Treatment Phase (of 14 Days) of the trial.

CONFIDENTIAL Page 20 of 31

Private and Confidential Study No 21755 Date: DEC 18, 2023

The primary efficacy analysis population will be PP population and ITT Population will be secondary. The same analysis on ITT Population will be repeated for the primary and secondary efficacy endpoints to assess the robustness of the results based on PP Population.

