This is a 14-day clinical trial (Treatment Phase) to test the hypothesis that Sitavig (acyclovir) buccal tablet safely and effectively reduces duration of a herpes labialis cold sore of the lip in immunocompetent adults. Eligible participants who pass screening procedures will be randomized and moved into the Run-in Phase. Participants will be randomly assigned one of two treatment groups - Sitavig (acyclovir) 50 mg buccal tablets or a placebo buccal tablet. The randomization assignment is such that there is a 1 in 2 chance of receiving the placebo treatment. Participants will have a 6 month eligibility window in which they can self-initiate treatment should prodromal symptoms start. At the start of prodromal symptoms, participants will self-

Version 5.0

Page: 17 of 68

initiate treatment and record face images as well as symptom scores over the next 14 days. Treatment consists of a single application (of the buccal tablet) beginning on Day 1. Face images and symptom scores are captured over the 14 day Treatment Phase.

Study Duration (Treatment Phase): 14 days

Study Duration (Follow up Phase): 12 months

Investigational Medicinal Product (IMP): Sitavig (acyclovir) 50 mg buccal tablet or placebo buccal tablet

Treatment Duration: 1 day

Visit Frequency: After the start of treatment, two visits within the 14 day Treatment Phase. Additional follow up by phone will occur at 3, 6, 9 and 12 months after treatment.

Condition/Disease: Herpes labialis of the lips caused by herpes simplex virus type 1 (HSV-1) or herpes simplex virus type 2 (HSV-2).

Study Hypothesis: Sitavig (acyclovir) buccal tablet effectively reduces the duration of a cold sore of the lips.

Health Measurement/Observation: Independent blinded lesion evaluation using a 6-point Likert scale and 0-10 NRS symptom scores will occur pre and post treatment.

Intervention Groups: Participants will be randomized in 1:1 fashion (active or placebo) with a single dose of study intervention.

Data Monitoring/Other Committee: No

Version 5.0 Page: 18 of 68

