^c Face images taken at 09:00, 14:00 and 19:00 each day.

^d The 2-day window pertains to all Visit 3 tasks except the NRS symptom scores, face images, QoL-OHIP and Global assessment which should be collected at their respective nominal times (±60 minutes) on Day 14.

^e Face image(s) and NRS symptom score(s) required if a new outbreak of herpes labialis is suspected by the investigator.

^f After successful completion of all screening procedures.

^g Follow up dates established using the Day 1 dosing date.

Version 5.0 Page: 20 of 68

2. Introduction

Herpes labialis (HL), also called cold sores of the lip, is an infection primarily caused by herpes simplex virus type 1 (HSV-1) and occasionally herpes simplex virus type 2 (HSV-2). The infection is typically spread between people by direct contact. HL is a rash of the skin and mucous membranes (in particular, the lips) and is characterized by erythema and blisters that are preceded and accompanied by tingling, itching or burning pain [1].

For an infection to manifest, the virus must come in contact with mucosal surfaces or abraded skin. The viral replication takes place at the site of primary infection (epithelial cells), either as an intact virion or the capsid is transported in a retrograde fashion by neurons to the dorsal root ganglia, where, after another round of viral replication, latency is established. After primary infection, the virus recedes via the sensory nerve into the respective ganglion (usually the trigeminal ganglion), where it lies latent throughout the individual's lifetime. Stimuli such as fever, menstruation, sunlight, and upper respiratory infections can reactivate the virus, after which it returns to the epithelial cells via the sensory nerve [2].

HSV1 and HSV2 infections rest in a dormant (inactive) state until the virus is activated. During an active phase of infection, a visible outbreak of sores may be observed. Infrequently, life-threatening infection (e.g., encephalitis) may occur. The more severe the primary infection (as reflected by the size, number, and extent of lesions) the more likely it may be that recurrences may develop when triggered [3,4].

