4.1.1.4 Follow-up Phase

Participants will automatically transition to the Follow-up Phase after the completion of the Treatment Phase. Participants will be in contact with the Science 37 using weekly virtual check-ins within the Science 37 Platform with the purpose reporting any adverse events, concomitant medications or new outbreaks of HL. Potential new HL occurrences will be reviewed by the investigator using face images and symptom scores.

The duration of each patient's participation will be up to 20 months. For an overview on the trial design and trial procedures see Section 1.2.

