4 DEFINITIONS AND DERIVATIONS

Run-in Failures: Run-in failures are participants who successfully completed screening and randomized to a blinded study intervention (treatment). Participants start a 6-month eligibility window during the Run-in Phase where they could potentially self-initiate treatment. Participants who are considered a Run-in failure occur because of the following:

- Randomized participants with no prodromal symptoms after 6 months
- Met an exclusion criterion (e.g., medication, pregnancy)
- Adverse event or change in medical history that requires study withdrawal
- Withdraw of informed consent by the participant
- Study intervention kit not available
- Lack of compliance as determined by the Investigator/designee

Baseline: Baseline value is defined as the last non missing assessment prior to first administration of the study drug. If the assessment occurs on the same day as the first study drug administration, then the time of assessment should be compared to the time of first dose administration to derive the baseline value.

Post-baseline: The Post-baseline values are defined as assessments taken after the first administration of study drug/treatment.

Change from Baseline = $(post\ baseline\ value - baseline\ value)$.

Duration of Episode (DOE): DOE is defined as the time from the initiation of treatment to the healing of primary lesions (loss of crust) for subjects who experience a vesicular lesion. For subjects whose primary lesions are not vesicular in nature, DOE is the time from study intervention initiation to the return to normal skin as determined by the independent blinded reader of the subject's face images using a 6-point Likert scale or the cessation of symptoms, whichever comes last. For the subjects who do not demonstrate the healing of primary lesions or cessation of symptoms, the data will be censored at 14 days (14*24 hours) regardless of any circumstances. If time (hour) is missing for either treatment initiation or the healing of primary lesion or both, however, both dates are recorded, then DOE is number of days (end date – start date) *24. If only healing ending date and/or time are missing, DOE will be imputed as 14*24 hours. If date of treatment initiation is missing, then DOE will be missing.

CONFIDENTIAL Page 17 of 31

Private and Confidential Study No 21755 Date: DEC 18, 2023

DOE (hours) = (Date and time of healing of primary lesions – Date and time of first treatment administered)

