Vesicular lesion: A lesion will be categorised as vesicular if a subject has face image interpretation Likert scale score of 3 or above.

Healing of primary lesions: A vesicular lesion will be considered as healed if the face image interpretation Likert score drops to either 0 or 1 after progressing to 3 and beyond. For those without a vesicular lesion, healing is defined as a face image interpretation Likert score of 0 or cessation of symptoms i.e., all NRS symptom scores as 0, whichever comes last.

Cessation of symptoms: Cessation of symptoms is defined as the absence of sensations of pain, tenderness tingling, itching or discomfort at the site of the cold sore as measured by NRS. In other words, having the NRS score of 0 for all symptoms such as pain, tingling, tenderness, itching and discomfort is cessation of symptoms.

Time to cessation of symptoms: It is the time (in hours) from the initiation of treatment dose of assigned study intervention to cessation of symptoms. For the subjects who do not demonstrate the cessation of symptoms, the data will be censored at 14 days (14*24 hours) regardless of any circumstances. If hour is missing for either treatment initiation or the endpoint but both dates are recorded, then Time to cessation of symptoms is number of days (end date – start date) multiplied by 24. If either date is missing, then Time to cessation of symptoms is missing.

 $\it Time\ to\ cess at ion\ of\ symptoms = (Date\ and\ time\ of\ cess at ion\ of\ symptoms - Date\ and\ time\ of\ first$

treatment administered)

Time to recurrence of HL lesions: It is the time (in days) from resolution of the cold sore treated in the Treatment phase until appearance of a cold sore during the follow-up period. The time to first recurrence is determined by assessment from the investigator and documented using NRS symptom scores and face images using the Science 37 Platform. For subjects who do not recur during the follow-up period, the data will be censored at the time of last follow-up.

Time to recurrence of HL lesions (Days) = (Date of first recurrence of HL lesions – Date of healing of primary lesions) + 1

CONFIDENTIAL Page 18 of 31

Private and Confidential Study No 21755 Date: DEC 18, 2023

Treatment Emergent Adverse Event: A TEAE is defined as any new AE that commences on or after the start of the first study drug administration or any pre-existed AE/ condition that worsened in severity following administration of study drug.

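### The Follow-Up population's 'all treated' clause is either empty or selects on healing, the primary endpoint's event, and should be deleted from the SAP's recurrence analyses

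*SAP*

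**What the plan says.** SAP 6.1 builds the Follow-Up set in two steps. The first is "The Follow Up population will be a subgroup of the ITT population who will continue into the 12 month follow up period". The second is that members are "defined as patients whose lesions were all treated at the end of the Treatment Phase", with the phase given as 14 days. The word 'treated' is not defined there or in SAP section 4.

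The parent set already requires a dose. ITT is "All subjects who are randomized and provide at least one measure of primary efficacy parameters after the first dose of IMP", which SAP 6.1 explains as at least one face-image reading after study drug. On dosing, Protocol 1.1 says "Treatment consists of a single application (of the buccal tablet) beginning on Day 1".

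SAP 7.7.2 uses the Follow-Up set for the test of the percentage with at least one recurrence and for the Kaplan-Meier analysis of time to recurrence. In SAP section 4 that time is the date of first recurrence minus "Date of healing of primary lesions) + 1".

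Protocol 9.3 (Table 2) lists Safety, ITT and Per Protocol sets only. Protocol 4.1.1.4 says "Participants will automatically transition to the Follow-up Phase after the completion of the Treatment Phase", with no condition on the lesion. SAP 7.13, the list of departures from the protocol, mentions only that recurrence incidence will be counted and not tested.

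**The concern.** A set used to compare randomised arms should not depend on something that happens after randomisation and that the treatment may alter. Healing is exactly that: "DOE is defined as the time from the initiation of treatment to the healing of primary lesions (loss of crust", observed for up to 14 days, and the study hypothesis is that the drug shortens it. If the clause means healed by Day 14, unhealed participants are dropped, and if the drug works more of them come from placebo. The two arms of the recurrence comparison then differ in composition even if the drug has no effect on recurrence.

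If the clause means dosed, no such selection arises. But participants unhealed at Day 14 then stay in the set, and the time-to-recurrence formula gives them no start date.

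Two programmers could build different sets from this sentence and report different p-values for an outcome that Protocol 2.2 singles out as a notable result of the previous trial.

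**Working it through.** The plan states no figure that can be reproduced here: the sample-size text is redacted and no healing or recurrence rate is given. The check is therefore a comparison of the passages, followed by an illustration on assumed inputs.

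**Reading 1: treated means dosed.** Elsewhere the SAP uses the word this way, for example for the treated lesion in the primary endpoint (SAP 5.1). Every ITT member has been dosed and the only dose is on Day 1, so the clause removes nobody. A participant unhealed at Day 14 is censored for the primary endpoint at 14 × 24 = 336 hours, but the SAP does not say that this time, or any other, serves as the origin for time to recurrence. The censoring rule for that endpoint covers only participants who do not recur.

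**Reading 2: treated means healed.** The reference to status at the end of the 14 days points this way. The set is then ITT, continuing into follow-up, and healed by Day 14. The 336-hour censoring rule shows that some non-healing is expected.

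**Size under reading 2.** All inputs are assumptions. Let p0 and p1 be the proportions healed by Day 14 on placebo and Sitavig. Assume that anyone who would heal by then on placebo would also heal on Sitavig. Let rA be the recurrence risk in those who heal on either arm and rB the risk in those who heal by Day 14 only on Sitavig. Suppose the drug has no effect on recurrence in either group.

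- Placebo, healed set: recurrence = rA.
- Sitavig, healed set: recurrence = [p0·rA + (p1 − p0)·rB] / p1.
- Spurious difference = [(p1 − p0)/p1] × (rB − rA).

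Worked case, with p0 = 0.80, p1 = 0.90, rA = 0.65, rB = 0.85: (0.80 × 0.65 + 0.10 × 0.85)/0.90 = 0.605/0.90 = 0.672, and 0.672 − 0.65 = 0.022, or 2.2 points. With rB = 0.45 it is −2.2 points.

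The type I error below is for the pooled two-proportion z-test at two-sided 0.05, with 150, 300 and 500 participants per arm before exclusions (also assumed), rA = 0.65 and rB = 0.85:

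| p0, p1 | Excluded, placebo / Sitavig | Spurious difference | Type I error, 150 / 300 / 500 |
|---|---|---|---|
| 0.80, 0.90 | 20% / 10% | 2.2 points | 0.066 / 0.083 / 0.105 |
| 0.90, 0.95 | 10% / 5% | 1.1 points | 0.054 / 0.058 / 0.063 |
| 0.95, 0.97 | 5% / 3% | 0.4 points | 0.051 / 0.051 / 0.052 |

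If p1 = p0 or rB = rA, the difference is 0. With no condition on healing, this selection term vanishes and the error stays at 0.050 under the same assumptions.

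**Direction.** The sign follows rB − rA, which is unknown. Selection can also hide a difference. Suppose 10% of placebo and 5% of Sitavig are unhealed, and slow healers recur at 95% against 85% for the rest. The full arms then have 0.90 × 85% + 0.10 × 95% = 86.0% and 0.95 × 85% + 0.05 × 95% = 85.5%. The healed-only sets have 85.0% each.

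**The case against.** The strongest reply is that the SAP says 'healed' or 'healing' when it means that, and 'treated' for lesions given study drug. On its own vocabulary the set is simply ITT participants who continue into follow-up, close to Protocol 4.1.1.4, and nothing is selected on healing. This has weight, but it does not explain why a status at the end of the 14 days is invoked for a single Day 1 dose, and no passage settles the meaning. It also leaves unhealed participants without a time origin.

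A reader might infer more than the documents support:

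- *That recurrence is analysed only in this set.* SAP 6.1 and Protocol 9.3 promise an ITT repeat for the secondary efficacy endpoints. The mitigation is partial: the stated purpose is robustness of the Per Protocol results, and SAP 7.7.2 names ITT and PP for aborted lesions but only the Follow-Up set for recurrence.
- *That the set excludes nobody under reading 1.* Only the clause is empty. The set still requires continuing into follow-up.
- *That the protocol carries everyone into follow-up.* Transition follows completion of the Treatment Phase, and Protocol 6.4 removes participants unblinded in follow-up from the follow-up analysis.
- *That time to recurrence should simply be re-timed from dosing.* Protocol 9.4.3 starts that endpoint at resolution, so some dependence on healing belongs to the endpoint itself. The avoidable selection is clearest for the percentage with recurrence.
- *That the bias is large or favours the drug.* Protocol section 2 describes blisters as lasting around 7 to 10 days, so few may be unhealed at Day 14, and the direction cannot be known.

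**Conclusion.** The point holds as a defect in the definition of a secondary analysis set. The clause either does nothing or conditions the recurrence comparison on the primary endpoint's event. It has no counterpart in the protocol and is not declared as a change.

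The size is unknown. Under the assumptions above it runs from near zero, if about 95% or more heal by Day 14 on both arms, to about 2 points with type I error of 0.066 to 0.105 in the most extreme case tried. Those figures rest on assumed healing rates, recurrence risks and arm sizes. The primary analysis is not touched. The change is worth making because it costs almost nothing and removes an avoidable selection from the recurrence-percentage test.

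**What to change.** - **SAP 6.1:** delete the 'all treated' clause. Define the Follow-Up population as all ITT participants who enter the Follow-up Phase, whatever their healing status at Day 14, subject to the exclusion in Protocol 6.4 of participants unblinded in follow-up.
- **SAP 7.7.2:** test the percentage with recurrence in that set and repeat it in ITT, so that 7.7.2 agrees with 6.1. State how ITT participants who never enter follow-up are counted in the repeat.
- **SAP section 4:** keep time to recurrence from healing as the protocol-defined analysis, and state that participants with no healing date by Day 14 have no origin for it. Add a sensitivity analysis timed from Day 1 dosing that includes everyone in the set. That date exists for every dosed participant and already anchors the calls: "Follow up dates established using the Day 1 dosing date".
- **SAP 7.13:** list the Follow-Up set as an addition to the protocol.

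Protocol 9.5 places the treatment-phase analysis before the follow-up analysis, so the wording is best settled before healing results are seen.

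The cost is SAP text and a little extra analysis. The from-dosing time includes the treated episode, so faster healing shortens it for the same healing-to-recurrence interval; that is why it should be a sensitivity analysis and not the main one. Entry into follow-up remains a post-randomisation condition, which the ITT repeat helps to probe.

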6.2 Treatment Groups

In this study there are two treatment groups:

- Sitavig® (acyclovir) 50 mg muco-adhesive buccal tablet (one tablet application on Day 1).
- Placebo muco-adhesive buccal tablet (one tablet application on Day 1).

The treatment groups will be labelled as "Sitavig" and "Placebo" in the TLFs.

7 ANALYSES METHODS AND REPORTING DESCRIPTIONS

7.1 Subject Disposition

Subject disposition for screened population will summarize the number and percentage of subjects screened, screen failure, subjects randomized, subjects in Safety, ITT, PP, and FU populations, who completed the study, and who prematurely discontinued the study along with the reasons for discontinuation and withdrawal from study by treatment groups.

Individual subject data on disposition will be presented in listing.

7.2 Demography and Baseline Characteristics

The demographic and baseline characteristics will include age (years), gender, ethnicity, race, height (cm), weight (kg), and BMI (kg/m2) will be summarized by treatment group for ITT Population. Continuous variables will be summarized using descriptive statistics (n, mean, SD, minimum, median and maximum) and for categorical variables, the number and percentage of subjects in each category will be summarized.

Individual subject data listings for demographic and baseline characteristics will be presented.

